5.2.1 DBT Interpretation

DBT interpretation will be performed during the course of routine clinical practice by radiologists using the standard of care American College of Radiology BI-RADS lexicon.³³ For the initial screen, BI-RADS categories of 0 (incomplete), 1 (negative), or 2 (benign) will be assigned. Interpretive findings, including lesion type, size, and location will be abstracted from the clinical

DBT report by study staff. A study radiologist will review the DBT exams with BI-RADS assessment 0 and assign a lesion ID and per-lesion assessment category for each lesion identified on the clinical DBT screening report. Categories 3, 4, and 5 are considered test positive.

5.2.2 MBI interpretation

MBI exams will be interpreted by study radiologists who have interpreted at least 50 MBI exams and/or have completed the American College of Radiology web-based training module. Study radiologists are required to pass an MBI interpretation quiz prior to interpreting study MBI examinations. MBI examinations will be assessed according to the established MBI lexicon³⁴ with assessment codes as follows: category 1, negative; category 2, benign; category 3, probably benign; category 4, suspicious for malignancy; category 5, highly suggestive of malignancy. A per-lesion assessment category will be assigned. Categories 3, 4, and 5 are considered test positive.

5.3 Diagnostic Workup of Screening Findings

Any diagnostic work-up imaging recommended from either screening study (DBT or MBI) will be postponed until completion of both blinded imaging study interpretations. If additional imaging is recommended on the basis of either DBT or MBI, an integrated interpretation will dictate further diagnostic evaluation.

Workup of DBT findings should be performed according to standard of care. MBI findings are allowed to generate additional diagnostic workup in the setting of a negative or benign assessment on DBT screening. However, a negative or benign assessment on MBI screening should not change recommendations generated by test-positive DBT.

The recommended diagnostic workup for DBT and MBI findings is detailed in Figures 2 and 3. For test-positive DBT findings, diagnostic mammography and/or targeted ultrasound will be performed as appropriate (Figure 2).

For test-positive MBI findings in the setting of a test-negative DBT screen, workup may include diagnostic mammographic views and/or targeted ultrasound and/or diagnostic MRI, as appropriate (Figure 3). If no suspicious correlate is seen on diagnostic mammogram or ultrasound for a lesion with assessment category 3 on MBI, a 6 month follow-up MBI is recommended. Lesions seen on MBI with assessment category 4 or 5, in the absence of a mammographic or sonographic correlate accounting for the MBI finding, would prompt a breast MRI.

[figure not shown]

Figure 2: Diagnostic workup for lesions with positive DBT (assessment 3, 4, or 5) and any MBI assessment at initial screening. MG = mammogram; US = ultrasound

[figure not shown]

Figure 3: Diagnostic workup for lesions with negative DBT (assessment 1 or 2) and positive MBI (assessment 3, 4, or 5) at initial screening. MG = mammogram; US = ultrasound

6. ADVERSE EVENT REPORTING

An adverse event (AE) is generally defined as any unfavorable and unintended diagnosis, symptom, sign (including an abnormal laboratory finding), syndrome or disease which either occurs during the study, having been absent at baseline, or if present at baseline, appears to worsen. Adverse events are to be recorded regardless of their relationship to the study intervention.

As per NCI Common Terminology Criteria for Adverse Events (NCI CTCAE) version 4.0 toxicity is defined as adverse events that are classified as either “possibly,” “probably,” or “definitely related” to the study.³⁵ The maximum grade for each type of toxicity will be recorded for each patient, and frequency tables will be reviewed to determine toxicity patterns. In addition, we will review all adverse event data that are graded as 3, 4, or 5 and classified as either “unrelated” or “unlikely to be related” to study assignment in the event of an actual relationship developing. Adverse events and toxicities will be evaluated using all patients who have undergone any study imaging; summaries of those who have been included in the efficacy analyses will also be provided.

All adverse events will be reviewed that are presented through study staff’s EPIC in-basket or Electronic Medical Record. Only those events that are determined by the Principal Investigator to be related to any aspect of the research will be documented and reported. Events that are not attributed will not be included in the study data and reported. However, all subjects will be asked to continue to report any adverse events.

A serious adverse event (SAE) is generally defined as any untoward medical occurrence that:

1. results in death
2. is life threatening
3. requires inpatient hospitalization or prolongation of existing hospitalization
4. results in persistent or significant disability/incapacity
5. results in a congenital anomaly.

All study subjects will be given a wallet card with the study team contact information 24/7. They will be educated on contacting the study team if any of these events occur. This will allow the study staff to be contacted if a serious adverse event occurs between study visits (up to 365 day time span).

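### Section 6 promises to record adverse events whatever their cause and to re-review unrelated grade 3-5 events, but its related-only documentation rule keeps unattributed events out of the study data; section 7 also drops women with only one baseline test from section 6's safety set

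*Combined protocol and SAP*

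**What the plan says.** Section 6 (Adverse Event Reporting) deals with event handling in three paragraphs.

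- **Paragraph 1** gives the recording rule: "Adverse events are to be recorded regardless of their relationship to the study intervention".
- **Paragraph 2** defines toxicity as an event judged possibly, probably or definitely related. It then says "we will review all adverse event data that are graded as 3, 4, or 5 and classified as either" of two classes, namely unrelated or unlikely to be related. The relationship in view, and the reason for the review, are given as "to study assignment in the event of an actual relationship developing". The paragraph also sets the population: "Adverse events and toxicities will be evaluated using all patients who have undergone any study imaging", and "summaries of those who have been included in the efficacy analyses will also be provided".
- **Paragraph 3** begins "All adverse events will be reviewed that are presented through study staff", the channels being their in-basket and the electronic record. It continues "Only those events that are determined by the Principal Investigator to be related to any aspect of the research will be documented and reported", and then "Events that are not attributed will not be included in the study data and reported".

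Section 7 (Duration of Follow-up) says that a woman who completes just one of the two baseline tests leaves the study and that nothing is collected on her. Section 8.4 separately restricts the Analysis Set for each screening year to eligible enrolled women who completed both DBT and MBI.

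**The concern.** Study staff are given opposite instructions on which events to write down. The paragraph 2 review exists to catch a relationship that was not apparent when an event was first attributed, and it is the only later check on that attribution that the documents describe. It needs events that already carry a grade and an attribution, and paragraph 3 keeps such events out of the study data when they are not attributed to the research. Section 4 plans several sites, so the two rules could be applied differently between them.

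The second conflict concerns who is counted. Section 6 promises a safety evaluation based on exposure to study imaging. Section 7 removes some imaged women and their data.

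**Working it through.** No formula applies and there is no plan figure to reproduce. The check sets the passages side by side.

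1. **Recording against documenting.** Paragraph 1 makes recording independent of relationship. Paragraph 3 makes documentation depend on the Principal Investigator's judgement of relationship. An event judged unrelated must be recorded under the first rule and must not be documented under the second.

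2. **Can *documented* mean only outside reporting?** No. The next sentence of paragraph 3 refers to the study data themselves, so the restriction reaches the dataset.

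3. **Can *recorded* mean noted in the medical record?** That would soften the clash with paragraph 1 but would not make paragraph 2 workable. Paragraph 2 describes events already graded and classified, and a chart note need not carry a study grade or attribution.

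4. **Does another passage reconcile the rules?** None does.
   - The serious adverse event text in section 6 gives a definition and a contact route but no recording rule of its own, so a serious event judged unrelated also falls under paragraph 3.
   - Section 8.1.3 records the date and cause of any death, but to settle breast cancer status and length of follow-up. It mentions neither grade nor attribution.
   - The reference standard in section 8 captures breast cancer diagnoses for the same limited purpose.
   - Section 8.9 plans no formal interim safety analysis.

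5. **Safety population.** Take a woman who completes DBT but not MBI at Year 1. Table 1 lists DBT among the study exams, so she has had study imaging and section 6 counts her. Section 7 leaves no data on her. Both cannot hold.

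6. **Where this has substance.** Section 5.1.2 allows a woman with confirmed infiltration of the injected dose to stop MBI, which ends her participation. If this happens at Year 1 and she has completed DBT, she has received the radiotracer, belongs to section 6's safety set, and under section 7 may leave no safety data, not even for a related event.

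7. **What is untouched.** Sections 2.1 and 2.2 list no safety endpoint. The primary test (section 8.5) and the sample size (section 8.7) use detection of invasive cancer only.

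**The case against.** Four arguments narrow the point.

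**The wording differs between paragraphs.** Paragraph 1 speaks of the study intervention, paragraph 2's review of study assignment, and paragraph 3 of the research in any respect, which is the widest. An event judged unrelated to assignment but related to some other part of the research would be documented and would still fall within the review. Paragraph 3 also never says that an event classed as unlikely counts as not attributed. A reader might infer that the documented and reviewed events have no overlap at all. The text does not establish that, and the conclusion here is limited to little or no data.

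**Source-level review remains possible.** Paragraph 3 has staff look at all incoming events and does not restrict that look to attribution. Paragraph 2 speaks of event data, not of a database. A reader might infer that severe unrelated events are lost; they are not, because the source records persist. What is missing is a graded, attributed set of study data, which makes later retrieval harder but not impossible.

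**The section 7 conflict is narrow.** It covers one baseline test only. Section 5.1 makes Year 2 DBT optional, and a woman with MBI alone at Year 2 is not excluded. A woman with DBT only who never starts MBI has had a routine examination and no radiotracer. A reader might also take section 6's separate summaries for efficacy patients as proof that women with one baseline test were meant to be included. They prove nothing of the kind: section 8.4 also requires eligibility and both tests in each year, so the safety set is wider than the efficacy set even with section 7 in force.

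**The consequences are small.** Section 1.4 describes a long and favourable safety record for the tracer, related toxicities are still tabulated, and no efficacy result depends on these rules. That limits the importance of the point. It does not remove the contradiction, because a plan that promises a review should leave the data with which to carry it out.

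**Conclusion.** Wrong as written, for safety data only. Section 6 contradicts itself on which adverse events enter the study data, and its promised review of unrelated grade 3-5 events would have little or no graded, attributed study data to draw on. Section 7 also conflicts with section 6's safety population for women with only one completed baseline test.

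The first conclusion rests on the plain wording of section 6 and is firm. The second assumes that section 7's exclusion applies to safety data as well as efficacy data; section 7 does not name the safety set, but its wording makes no exception.

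The size cannot be expressed as a count. The documents give no adverse event rate and do not say how many women will complete a single baseline test. Section 5.1.2 gives a frequency for infiltration but not for stopping afterwards. Nothing here supports a reading that the primary or secondary endpoints, the sample size or the power are compromised.

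**What to change.** Reconcile the passages by changing wording in two places.

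1. **Section 6.** Choose one rule.
   - *Keep the review.* Amend the two restrictive sentences of paragraph 3 so that the events paragraph 2 promises to review (at least every grade 3-5 event reaching study staff, whatever its attribution) are entered in the study data with grade and attribution. Align paragraph 1 to the same scope. Paragraph 2 can then stand as it is.
   - *Record related events only.* If that is the sponsor's intention, withdraw the sentence in paragraph 1 that makes recording independent of relationship, and withdraw the promised review in paragraph 2.
2. **Section 7.** Limit the exclusion for a single baseline test to the efficacy Analysis Set of section 8.4, so that women with any study imaging stay in the safety evaluation as section 6 states. Section 8.4 already requires both tests, so the efficacy analysis does not change.

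**Cost.** Keeping the review adds some records for staff who already look at incoming events. Their number cannot be estimated: the documents give no event rate and fix no collection window for adverse events (the serious-event contact text mentions up to 365 days between visits, while the 30 months in section 7 are for breast cancer status). Related-only recording adds no records but gives up the later check. The section 7 change means keeping safety data on a group of women whose number the documents do not state.

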7. DURATION OF FOLLOW-UP

Study participation involves 2 study visits for breast screening – one at the beginning of the study and a second visit one year later. Participants will be enrolled in the study for approximately 2.5 years (30 months) to ascertain breast cancer status, and may be contacted at the end of study if breast cancer status cannot be ascertained based on chart review, alone. If only one of the baseline

imaging tests (DBT or MBI) is completed, the patient will be excluded from the study and no data will be collected. Participant's breast cancer status will be obtained from chart review or patient contact targeted for 365 days after each screening year, but may be obtained from 335 days to 455 days after screening, unless the patient specifically requests to withdraw from the study. If a patient is diagnosed with a primary breast cancer during the study period, no subsequent follow-up or further study imaging will be required for this research study.

8. STATISTICAL CONSIDERATIONS

8.1 Study Design

This study employs a paired design in which all participants will undergo both DBT and MBI for two rounds of annual screening, defined as Year 1 and Year 2. Unless otherwise specified, the primary unit of analysis will be the patient.

8.2 Reference Standard

A study participant can be classified as having either positive or negative breast cancer status in a given screening year.

8.1.2 Establishing Year 1 Reference Standard

Positive Breast Cancer Status for Screening Year 1 is established if one of the following is true:

- A participant has a histopathologic diagnosis of breast cancer^a within the time period from Year 1 screening^b until Year 2 screening^c, not including Year 2 screening
- A participant does not undergo Year 2 screening^c but has a histopathologic diagnosis of breast cancer^a within 365 days of Year 1 screening.

Negative Breast Cancer Status for Screening Year 1 is established by any of the following, in order of best to least reliable determination:

1. A participant has both Year 2 screening MBI and DBT, both with negative or benign findings, or positive findings that are ultimately determined to be benign after diagnostic imaging workup or tissue diagnosis.
2. A participant does not complete both Year 2 screening MBI and DBT, but is followed through chart review or patient contact, resulting in documentation of any breast imaging test performed at least 335 days after Year 1 screening, with negative or benign findings, or positive findings that are ultimately determined to be benign after diagnostic imaging workup or tissue diagnosis.
3. A participant does not undergo Year 2 screening but is contacted at least 335 days after Year 1 screening and the participant herself confirms that she did not have a breast cancer diagnosed that meets the Positive Breast Cancer Status definition.
4. A participant does not undergo Year 2 screening but is followed through chart review at least 335 days after Year 1 screening and no breast cancer is reported to meet the Positive Breast Cancer Status definition.

A participant with breast cancer detected on Year 2 screening is assumed to have negative breast cancer status for Year 1 and the cancer diagnosis is included in the Year 2 analysis, not the Year 1 analysis.

8.2.2 Establishing Year 2 Reference Standard

Positive Breast Cancer Status for Screening Year 2 is established if one of the following is true:

- A participant has a histopathologic diagnosis of breast cancer^a within the time period from Year 2 screening until the next annual screen (Year 2), not including the next annual screen.
- A participant does not undergo Year 2 screening^d but has a histopathologic diagnosis of breast cancer within 365 days of Year 2 screening.

Negative Breast Cancer Status for Screening Year 2 is established by any of the following, in order of best to least reliable determination:

1. A participant is followed through chart review or patient contact, resulting in documentation of any breast imaging test performed at least 335 days after Year 2 screening, with negative or benign findings, or positive findings that are ultimately determined to be benign after diagnostic imaging workup or tissue diagnosis.
2. A participant does not undergo Year 2 screening^d but is contacted at least 335 days after Year 2 screening and the participant herself confirms that she did not have a breast cancer diagnosed that meets the Positive Breast Cancer Status definition.
3. A participant does not undergo Year 2 screening^d but is followed through chart review at least 335 days after Year 2 screening and no breast cancer is reported to meet the Positive Breast Cancer Status definition.

A participant with breast cancer detected on Year 2 screening is assumed to have negative breast cancer status for Year 2.

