5. IMAGING

5.1 Imaging Procedures

At Year 1 screening, all patients will undergo both DBT and MBI targeted to be performed on the same day if possible and required to be completed within three business days of each other prior to initiation of any diagnostic workup. All patients who did not receive a diagnosis of breast cancer during Year 1 will undergo subsequent annual MBI targeted to be performed at approximately one year (Year 2 screening) after Year 1 screening; and should be targeted for 335 to 455 days from Year 1 MBI screening. The Year 2 MBI should be scheduled within 3 business days of the Year 2 DBT if possible; completion of Year 2 DBT is encouraged but not required.

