8.6 Secondary Endpoints

- 1. To compare the rate of detection of invasive cancers between DBT alone vs. MBI alone at Year 1 screening.**

The comparison will be based on a 2-sided McNemar's test at statistical significance level alpha= 0.05.

2. To compare the screening performance metrics of sensitivity, specificity, recall rate, biopsy rate, positive predictive value and negative predictive value for DBT and MBI.

For both years of the study imaging (Year 1 and Year 2), the following secondary endpoints will be analyzed to compare performance of

- DBT alone vs. MBI alone, and
- DBT alone vs. the combination of DBT with supplemental MBI.

Sensitivity will be estimated for each modality as the proportion of women with breast cancer who have true positive test results. **Specificity** will be estimated as the proportion of women without breast cancer who have TN test results. Uncertainty in the estimate of sensitivity will be quantified through a two-sided 95% confidence interval (CI) based on the binomial distribution. If a sufficient number of radiologists interpret exams from multiple patients with breast cancer, secondary analysis may also include a 95% CI and chi-squared test adjusted for clustering of results within radiologist to allow generalization to both the population of patients and the population of radiologists.³⁶ For comparisons of DBT alone vs. the combination of DBT with supplemental MBI, a structural zero results due to the paired nature of the data and direct comparisons cannot be tested under a null hypothesis of equivalence. Analysis will alternatively focus on the conditional diagnostic odds ratio (cDOR) to quantify the added value of MBI over DBT alone.

Recall rate (defined as the proportion of patients recalled from the screening test for diagnostic workup among the total number of patients screened), and **biopsy rate** (defined as the proportion of patients in whom biopsy is generated from a particular modality among the total number of patients screened) will be estimated employing analytical strategies similar to sensitivity and specificity. McNemar's test will be used to compare rates between two modalities.

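### Without later imaging, a woman can be closed as cancer-negative from day 335 although positive status runs to day 365, so Year 2 sensitivity and NPV can be biased slightly upward

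*Combined protocol and SAP*

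**What the plan says.** Section 8.2.2 defines Year 2 status. It uses the label Year 2 for both the study screen and the annual screen after it, so it has to be read with footnote d (printed under Section 8.1.3). On that reading:

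- **Positive, no later imaging:** the woman "has a histopathologic diagnosis of breast cancer within 365 days of Year 2 screening".
- **Negative, item 1 (ranked most reliable):** "documentation of any breast imaging test performed at least 335 days after Year 2 screening" with a benign outcome. Footnote d makes clear that this imaging lies outside the study.
- **Negative, item 2:** the woman "is contacted at least 335 days after Year 2 screening and the participant herself confirms" that she had no qualifying cancer.
- **Negative, item 3:** the woman "is followed through chart review at least 335 days after Year 2 screening and no breast cancer is reported".

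Section 8.1.2, items 3 and 4, has the same two non-imaging routes for Year 1. Under item 4, for example, the woman "is followed through chart review at least 335 days after Year 1 screening and no breast cancer is reported". Section 7 targets ascertainment at day 365 "but may be obtained from 335 days to 455 days after screening". Sections 4 and 7 allow contact at the end of the study when the chart alone cannot settle status.

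The years differ in what follows the screen. After Year 1, Section 5.1 states: "All patients who did not receive a diagnosis of breast cancer during Year 1 will undergo subsequent annual MBI". After Year 2 there is no study visit. Section 8.6, item 2, nevertheless covers both years: "For both years of the study imaging (Year 1 and Year 2), the following secondary endpoints will be analyzed". Sensitivity and NPV are among those endpoints.

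**The concern.** The two definitions do not end on the same day. Day 335 is coherent for the imaging route, because there the positive window closes at that imaging. The contact and chart routes have no such end point. They rest on the absence of a cancer that meets the positive definition, and that cannot be fully checked before day 365. A woman reviewed on day 340 and diagnosed on day 360 can be recorded as negative, and the plan contains no step that would find or correct this.

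Most cancers lost in this way would have been missed by both tests, since screen-detected cancers are usually biopsied early in the year. They would leave the false negatives and join the true negatives, which raises sensitivity and NPV for DBT, for MBI and for the combination. In Year 1 the planned return visit closes the window for women who attend. Year 2 has no such visit and depends on outside imaging, charts or a call.

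**Working it through.** **1. The plan's own figures.** With an exact binomial test of 0.001 against 0.004 at one-sided alpha 0.025, N=2631 has critical count 7, exact alpha 0.0181 and power 0.9001 (2630 gives 0.8998). The sample size in Section 8.7 reproduces. The Section 8.6 rule of 7 or more interval cancers also reproduces at N=2631: the Clopper-Pearson lower limit is 1.07 per 1000 for 7 cancers and 0.84 for 6. Neither figure depends on the Year 2 reference standard.

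**2. Inputs.** From the documents:
- interval-cancer rate in dense breasts, 0.89 per 1000 (Section 8.6, item 5);
- N=2631, DBT invasive detection 4.7 per 1000 and increment 4 per 1000 (Section 8.7);
- the 335- and 365-day limits (Sections 7, 8.1.2 and 8.2.2).

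Assumed, because the documents do not give them:
- a uniform hazard over the year;
- the share *s* of women closed without imaging on day 335;
- a combined Year 2 detection rate of 4.7 + 4 = 8.7 per 1000.

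**3. Cancers exposed.**
- Expected interval cancers in a year: 2631 × 0.00089 = 2.34.
- Share of the window after day 335: 30/365 = 8.2%.
- Upper bound, *s* = 100%: 2.34 × 30/365 = 0.19 cancers.
- *s* = 10%: 0.02 cancers. *s* = 30%: 0.06 cancers.
- If the hazard late in the year were doubled, the upper bound would be 0.38.

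**4. Effect on Year 2 DBT+MBI sensitivity.**
- All interval cancers counted: 8.7/(8.7 + 0.89) = 90.7%.
- Upper bound of the loss: 0.89 × 30/365 = 0.073 per 1000, so 8.7/(8.7 + 0.817) = 91.4%, a shift of 0.7 points.
- *s* = 10-30%: shifts of 0.07-0.21 points.
- Doubled late hazard with *s* = 100%: 1.4 points.

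The 8.7 is built from Year 1 planning rates. A lower Year 2 yield would make the shift in points larger but would not change the number of cancers lost.

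**5. Effect on NPV.** At most about 0.073 per 1000 women, or 0.007 percentage points.

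**6. Room for a later review.** A Year 2 screen as late as day 455 plus 365 days is day 820. With the full 455-day tolerance it is 455 + 455 = 910. Thirty months is about 913 days, so both fit.

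**The case against.** Five points can be made in defence of the plan.

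- **Outside imaging closes Year 2.** A reader might infer that Year 2 has no protection at all. That is not so: Section 8.2.2, item 1, closes the year on any breast imaging from day 335 and ranks that route first. Only women without such imaging who are reviewed before day 365 are exposed. The documents do not give their share. This stands, and it is why the conclusion is that misses can be, not will be, under-counted.
- **Day 365 is the target.** Section 7 aims at it, and day 335 is the edge of the tolerance. True, but the tolerance is expressly permitted.
- **A day-360 diagnosis is positive on the text,** because the negative routes presuppose no qualifying cancer. That is a fair reading once the diagnosis is known. It does not help if nobody looks again, and no sentence requires that.
- **Silent charts.** A reader might add women whose chart is empty after the screen and arrive at a loss well above 8.2%. That needs a share of silent charts, which the documents do not state. Section 8.1.3 also treats a woman with no chart information who cannot be reached as lost, and counts her as cancer-free. What remains is that item 3 does not say whether a chart with no entry after the screen suffices, so the end-of-study contact might not be triggered.
- **Little hangs on it.** A cancer missed by both tests leaves the ratio of the two sensitivities unchanged. No comparison of sensitivity or NPV between years is planned. Sampling error is far larger: an exact 95% interval for 23 of 25 cancers (assumed, close to the expected counts) runs from 74% to 99%. The Year 2 analysis set needs both tests while Year 2 DBT is optional, so actual counts may be smaller. All of this stands and limits the weight of the point.

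**Conclusion.** The mismatch is real and is in the current text for both years. For women without later imaging, the contact and chart routes can close a case up to 30 days before the positive window ends, with no override. The possible bias in sensitivity and NPV is upward, and Year 2 is the more exposed year.

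The size is small: at most about 0.2 of 2.3 expected cancers and about 0.7 points of DBT+MBI sensitivity if every woman were closed on day 335 without imaging, and 0.02-0.06 cancers if 10-30% were. These figures rest on a uniform hazard, N=2631, 0.89 per 1000 and an assumed 8.7 per 1000 detected. The exposed share is unknown.

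The Year 2 gap does not touch the primary endpoint (Year 1 detection), the sample size or the interval-cancer endpoint, which covers only the time between the Year 1 and Year 2 screens. This is a minor correction worth making because it is nearly free.

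**What to change.** - In Section 8.1.2, items 3-4, and Section 8.2.2, items 2-3, replace 335 by 365 days for the contact and chart-review routes. Leave the imaging routes at 335.
- In Section 7, set the ascertainment window for these two routes to 365-455 days.
- Add one sentence: a diagnosis later found to fall within the positive window overrides an earlier negative status.
- Where the chart has no entry after the screen, use the end-of-study contact already allowed in Sections 4 and 7 before closing the woman as negative.

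The cost is wording in three sections, a slightly later review and some extra calls. The schedule fits within the 30 months. One limit remains: a woman who cannot be reached and has no chart information is still counted as cancer-free under Section 8.1.3, and this change does not alter that.
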